14.3 Written Informed Consent Form

Stryker NV will provide a sample Informed Consent Form (ICF) to the Investigator to prepare for use at his/her site, attached as **Appendix D**. The ICF documents should be translated into the language(s) understandable to potential subject population(s).

Stryker NV and the reviewing IRB/IEC must approve the ICF before use at that site. The ICF must be in agreement with current Good Clinical Practices (GCP) guidelines, the Declaration of Helsinki, and the International Conference on Harmonization (ICH).

Before participating in the clinical trial, each subject or his/her legally authorized representative (LAR) must give written Informed Consent after the context of the study has been fully explained in a language that is easily understood by the subject or LAR. The subject or LAR must also be given the opportunity to ask questions and have those questions answered to his/her satisfaction.

Written Informed Consent must be recorded appropriately by means of the subject's, or LAR's dated signature. The consent process must be documented in the subject's medical chart. At U.S. sites, electronic informed consent may be utilized in accordance with FDA's Guidance on the Use of Electronic Informed Consent in Clinical Investigations if approved by the site's IRB.

Note - If approved by local ethics committee and country regulations, the investigator is allowed to enroll a patient if, the subject or the representative or person of trust is not available to sign. However, as soon as possible, the patient is informed and his/her consent is requested for the possible continuation of this research. (Not applicable to US. Sites.)

14.4 Amending the Protocol

This protocol must be followed exactly. It can be altered only by written amendments made by Stryker NV. Following appropriate approval by Stryker NV, the amended protocol will be submitted to the required regulatory agencies before being distributed to all participating sites. Each site must obtain IRB/EC approval before implementing the revised protocol.

14.5 **Protocol Adherence**

Prior to beginning the study, the Investigator must sign the Investigator Agreement and Signature page documenting his/her agreement to conduct the study in accordance with the protocol. An Investigator must not make any changes or deviate from this protocol, except to protect the life and physical well-being of a subject in an emergency. Each deviation from the protocol must be documented with the date and reason for the deviation and reported to Stryker NV as soon as possible, and to the IRB/EC per local guidelines and government regulations. Major and minor protocol deviations are defined within **Appendix B**.

Document Number: CDM10000146

15 Study Administration

15.1 Pre-Study Documentation Requirements

Prior to enrolling any subjects into the trial the site must complete all pre-study essential documents, and these must be confirmed to be on file with Stryker NV:

- Site PI's CV and current medical license
- An operator qualification form (statement of experience) for at least one operator
- W-9 (or equivalent in other countries) to facilitate payment
- A fully executed clinical trial agreement
- IRB/EC approval of the study and the Informed Consent Form
- Documentation of all required study training
- Documentation of a completed Site Initiation Visit

No site may begin enrolling subjects until they receive written approval/authorization from Stryker NV.

15.2 Record Retention

The Investigator will maintain all essential trial documents and source documentation, in original format, that support the data collected on the study subjects in compliance with the ICH/GCP guidelines. Documents must be retained for at least 2 years after the last approval of marketing application or until at least 2 years have elapsed since the formal discontinuation of the clinical investigation of the product. These documents will be retained for a longer period of time by agreement with Stryker NV or in compliance with other regulatory requirements. The Investigator will take measures to ensure that these essential documents are not accidentally damaged or destroyed. If for any reason the Investigator withdraws responsibility for maintaining these essential documents, custody must be transferred to an individual who will assume responsibility. Stryker NV must receive written notification of this custodial change.

15.3 Criteria for Terminating Study

Stryker NV reserves the right to terminate the study but intends only to exercise this right for valid scientific or administrative reasons and reasons related to protection of subjects. Investigators and associated IRB/EC will be notified in writing in the event of termination.

DBP	Diastolic Blood Pressure
DE	Distal Embolization
DMC	Data Monitoring Committee
DNR	Do Not Resuscitate
DRSAE	Device-related SAE
DWI	Diffusion Weighted Imaging
EC	Ethics Committee
EE	Efficacy Evaluable
ENT	Embolization to New Territory
ESO	European Stroke Organization
GCP	Good Clinical Practice
НСТ	Hematocrit
HI-I	Petechial hemorrhage type I
HI-II	Petechial hemorrhage type II
Hr/Hrs	Hour/Hours
IA	Intra-Arterial
ICA	Internal Carotid Artery

Document Number: CDM10000146

Rev: AD

Abbreviation	Full Term
ICA-T	Internal Carotid Artery Terminus
ICF	Informed Consent Form
ICH	Intracranial Hemorrhage
IFU	Instructions For Use
INR	International Normalized Ratio
IRB	Institutional Review Board
ITT	Intent-To-Treat
IV	Intravenous
IVH	Intraventricular Hemorrhage
IVRS/IWRS	Interactive Voice Response System / Interactive Web Response System
LAR	Legally Authorized Representative
LTFU	Lost To Follow Up
LVO	Large Vessel Occlusion
M-1	The initial horizontal segment of the MCA, prior to the first bifurcation or trifurcation
M-2	The portions of the MCA distal to the first bifurcation or trifurcation, but prior to the second bifurcation
MCA	Middle Cerebral Artery

Document Number: CDM10000146

Rev: AD

Abbreviation	Full Term
MR/MRI	Magnetic Resonance / Magnetic Resonance Imaging
MRA	Magnetic Resonance Angiography
mRS	Modified Rankin Scale
mTICI	Modified Thrombolysis in Cerebral Infarction
NIHSS	National Institute of Health Stroke Scale
PH-I	Parenchymal hemorrhage type 1
PH-II	Parenchymal hemorrhage type 2
РР	Per Protocol
PRSAE	Procedure-related SAE
РТ	Prothrombin Time
PTT	Partial Thromboplastin Time
PWI	Perfusion Weighted Imaging
rCBF	Relative Cerebral Blood Flow
RIH	Remote Intracerebral Hemorrhage
SAE	Serious Adverse Event
SADE	Serious Adverse Device Effect
SAH	Subarachnoid Hemorrhage

Document Number: CDM10000146

Abbreviation	Full Term
SBP	Systolic Blood Pressure
SICH	Symptomatic Intracranial Hemorrhage
TICI	Thrombolysis in Cerebral Infarction
TIMI	Thrombolysis in Myocardial Infarction
TLSW	Time Last Seen Well
tPA	Tissue Plasminogen Activator (alteplase)
UADE	Unanticipated Adverse Device Effect
UK	Urokinase
USADE	Unanticipated Serious Adverse Device Effect
WUS	Wake Up Stroke

Document Number: CDM10000146

Appendix B. Definitions

Access Site Complication: Complication related to the vascular access site for the index procedure including but not limited to bleeding, hematoma, pseudoaneurysm, tears, pain or occlusion. Some of these complications may require additional treatment such as blood transfusion or surgical repair.

Adverse Event (AE): Any unintended disease or injury or untoward clinical sign in a research subject. NOTE - This definition does not imply that there is a relationship between the adverse event and the device under investigation.

Device Malfunction/Nonconformity: The failure of a device to meet its performance specifications or otherwise perform as intended. Performance specifications include all claims made in the labeling for the device. The intended performance of a device refers to the intended use for which the device is labeled or marketed.

Device-Related Serious Adverse Event (DRSAE): Trevo device related vascular perforation or intramural arterial dissection, symptomatic ICH, embolization to a new territory, intraprocedural death, or device failure (*in vivo* breakage).

Distal Embolization (DE): Any downstream occlusion distal to the target artery lesion (TAL), into the target ischemic territory, is considered DE unless complete angiogram or pre procedure non-invasive imaging demonstrated patency of these distal branches.

Early Response: A NIHSS drop of ≥ 10 from baseline or an excellent score of NIHSS 0 or 1 at Day 5-7 / Discharge (whichever is earlier).

Embolization to New Territory (ENT): Embolization into a previously uninvolved area of the brain, e.g. ACA embolization during MCA-M1 thrombectomy procedure. In ICA terminus occlusion, any MCA or ACA occlusion post procedure is considered distal embolization (DE) and not ENT. However, if pre procedure patency of these previously uninvolved territories is documented by complete angiogram or pre-intervention non-invasive imaging, then it would be considered ENT.

Epidural hemorrhage: Blood between the dura mater and the arachnoid mater.

**Good Clinical Outcome:** A measure of neurologic functional outcome with a score of 0–2 on the modified Rankin Scale (mRS), usually assessed 90 days after treatment.

Intracranial hemorrhage: A hemorrhage, or bleeding, within the skull

Intramural arterial dissection: A tear or damage to the inner arterial wall that occurs during the index procedure. The intramural arterial dissection may be identified angiographically as minor radiolucent area to luminal filling defect on imaging.

Document Number: CDM10000146

Intraprocedure Mortality: Death occurring during the index thrombectomy procedure

Intra-ventricular Hemorrhage (IVH): Bleeding into the brain's ventricular system.

In vivo (breakage) device failure: Breakage of the Trevo device in the vasculature during the index procedure.

Medical Management: In broad terms, medical management as the label for the Control arm means no intra-arterial intervention with drugs or devices. Furthermore, after randomization, a subject cannot be placed on intravenous thrombolytic therapy. The specific implementation of best medical management should be consistently applied and in accord with the relevant AHA or ESO guidelines, as applicable in the country of treatment.

Modified Rankin Scale: Scale for measuring the degree of disability or dependence in the daily activities of people who have suffered a stroke or other causes of neurological disability.

Neurological worsening: A 4 or more point increase in NIHSS from baseline. Neurological worsening could be new or evolution/progression of the index stroke.

NIHSS Score: An assessment to objectively quantify the impairment caused by a stroke. It is composed of 11 items, each of which scores a specific ability between a 0 and 4. For each item, a score of 0 typically indicates normal function in that specific ability, while a higher score is indicative of some level of impairment. The individual scores from each item are summed in order to calculate a total NIHSS score. The maximum possible score is 42, with the minimum score being a 0.

Parenchymal hemorrhage type 1 (PH-1): A hematoma in \leq 30% of the infarcted area with some slight space-occupying effect.

Parenchymal hemorrhage type 2 (PH-2): Dense hematoma > 30% total of the infarcted area with substantial space-occupying effect or any hemorrhage area outside the infarcted area.

Petechial hemorrhage type I (HI-1): Small petechiae along the margins of the infarct.

Petechial hemorrhage type II (HI-2): More confluent petechiae within the infarcted area but without space-occupying effect

**Pre-stroke disability:** Obtained at baseline, but representative of the subject's status before the index stroke, assessed by mRS on medical history obtained from subject's medical chart, or family members.

Procedure-Related Serious Adverse Event (PRSAE): Procedure-related events that include, but are not limited to vascular perforation or intramural arterial dissection,

Document Number: CDM10000146

symptomatic ICH, embolization to a new territory, or access site complication requiring surgical repair or blood transfusion, intra-procedural death, or device failure (*in vivo* breakage).

**Protocol Deviation:** Any alteration/modification to the current IRB/EC-approved protocol. The protocol includes the detailed protocol, protocol summary, consent form, recruitment materials, questionnaires, and any other information relating to the research study. Note: Any permanent change to the protocol constitutes an amendment that must be submitted to the Institutional Review Board/Ethics Committee for approval prior to initiation. Deviations may be further classified as:

- Major deviation: a deviation that may impact subject safety, affect the integrity of study data and/or affect subject's willingness to participate in the study, such as but not limited to: enrollment without obtaining appropriate informed consent; violation of inclusion/exclusion criteria; randomization irregularities including treatment arm crossover; confounding procedure by using non allowed therapies; non reporting of SAEs/UADEs and study product non conformities; and protocol required assessments repeatedly not completed at the required time windows
- Minor deviation: a deviation that does not impact subject safety, compromise the integrity of study data and/or affect subject's willingness to participate in the study, such as but not limited to: follow up assessments not conducted or conducted outside of the required time windows.

Protocol Exception: Any single protocol deviation that is approved by Stryker NV prior to its initiation, and documented in writing. Note: Any permanent change to the protocol constitutes an amendment that must be submitted to the IRB/EC for approval prior to initiation.

Remote Intracerebral Hemorrhage (RIH): Any intraparenchymal hemorrhage remote from the ischemic field.

Serious Adverse Device Effect (SADE): Any serious adverse effect on health or safety or any life-threatening problem or death caused by, or associated with, a device, if that effect, problem, or death was not previously identified in nature, severity, or degree of incidence in the investigational plan or application (including a supplementary plan or application), or any other unanticipated serious problem associated with a device that relates to the rights, safety or welfare of subjects.

Serious Adverse Event (SAE): An adverse event in a research subject that led to a death, or led to a serious deterioration in the health of the subject that resulted in a life-threatening illness or injury, or resulted in a permanent impairment of a body structure or a body function, or required in-patient hospitalization or prolongation of existing hospitalization, or resulted in medical or surgical intervention to prevent permanent impairment to body structure or a body function. SAEs are a subset of AEs.

Document Number: CDM10000146

- NOTE 1 This definition does not imply that there is a relationship between the serious adverse event and the device under investigation.
- NOTE 2 A planned hospitalization/procedure for a pre-existing condition or a condition required by the protocol, without serious deterioration in health is not considered serious but should be recorded as an AE. Deterioration in health as a result of the planned hospitalization/procedure should be recorded as a new AE.

Stroke: An acute neurological event with focal symptoms and signs lasting \geq 24 hours. Stroke can be sub-classified as Hemorrhagic or Ischemic.

- **Hemorrhagic Stroke:** A symptomatic intracerebral, subarachnoid, or primary intraventricular hemorrhage. To be considered a hemorrhagic stroke, the patient must experience new symptoms (e.g., new severe headache) that last for at least 24 hours (symptoms do not need to be associated with a new neurological deficit).
- **Ischemic Stroke:** A neurological deficit that is thought to have an ischemic cause and is detectable on examination at least 24 hours after onset of symptoms.

Stroke-related Death: Death related to the index stroke; to systemic complications associated with the index stroke, or a new stroke.

Subarachnoid Hemorrhage (SAH): Bleeding into the subarachnoid space - the area between the arachnoid membrane and the pia mater surrounding the brain.

Subdural hemorrhage: Blood between the dura mater and the skull.

Symptomatic ICH (SICH): The primary protocol definition is adapted from ECASS III as any apparently extravascular blood in the brain or within the cranium that is associated with clinical deterioration as defined by an increase of four points or more in the NIHSS, or that led to death and was judged to be the predominant cause of a neurologic deterioration. The SITS-MOST definition of SICH is: Any PH-2 with a four point or more increase in NIHSS.

Unanticipated Serious Adverse Device Effects (USADEs): A subset of SADEs that are unanticipated, or not previously identified in the labeling of the investigational device, including the Investigator Brochure, Clinical Investigational Plan and Informed Consent Form

Vessel Perforation: A hole or puncture (perforation) in the vessel wall that occurs unintentionally during the index procedure. The perforations may be seen angiographically during the index procedure by frank or free extravasation of the contrast into the surrounding tissue or blush or localized contrast extending outside the vessel lumen.

Weighted mRS: A numerical value representing the clinical utility of each mRS category.

Document Number: CDM10000146

Rev: AD

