4.3 Primary Safety Outcome

Both Arms:

1. Incidence of stroke-related mortality at 90 days

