5.3 Method of Assigning Subjects to Treatments

Randomization will be accomplished at each site using either a block of randomization envelopes, or by using a commercially available Interactive Voice Response System (IVRS) or Interactive Web Response System (IWRS). Subjects will be randomized 1:1 to Trevo thrombectomy plus medical management or medical management alone. In order to ensure both groups are balanced, subjects will be stratified by Clinical Imaging Mismatch (CIM) subgroups (see Imaging Inclusion Criteria in **Section 6.1.1**), TLSW between 6 and ≤ 12 hours and >12 to 24 hours, and baseline occlusion location (ICA vs. M1). Enrollment in this study is defined as the moment when the randomization process is completed and the subject is assigned to a study arm. After randomization, no crossover is permitted.

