12.2 Investigational procedure (Treatment arm only)

12.2.1 **Diagnostic Angiography**

Risks associated with angiography have been well documented and are understood by the medical community. The arteriogram itself can cause problems with brain function and it can potentially make the subject's condition worse. Angiography requires the placement of an intra-arterial catheter for the injection of contrast media to image vessels in the brain, and the most common complication is access-site hematoma (4.2%). [102] Other risks related to the diagnostic angiographic procedure are relatively low but may include:

- Infection
- Bleeding
- Hematoma
- Vessel thrombosis
- Dissection
- Distal embolization
- Pseudoaneurysm and arteriovenous fistula formation
- Vessel injury
- Allergy to the contrast material
- Neurological injury

Document Number: CDM10000146

• Death

The risk of bleeding may be increased when diagnostic angiography is performed in individuals who are receiving anticoagulation and/or antiplatelet therapy. Neurological injury associated with these vascular complications may occur. Renal toxicity and idiosyncratic responses to the injected contrast medium including anaphylactic reactions have also been reported.

12.2.2 **Trevo Thrombectomy**

For any individual subject, participation and randomization to the treatment arm is no guarantee that they will receive a direct benefit. Completion of the study may benefit the subject's community at large through enhanced knowledge about the risks and benefits of these two treatment modalities: Trevo Retriever plus medical management versus medical management alone.

The potential risks associated with the use of the Trevo Retriever include:

- An air bubble introduced into the blood vessels (air embolism)
- Bleeding or bruising in the access site, or where the puncture is made (hematoma)
- Infection at the access site, or sepsis
- Embolization of a fragment, or the entire thrombus, to a previously uninvolved territory (emboli)
- Vessel spasm
- Pain/headache
- New clot formation (thrombosis)
- A blood vessel tear or puncture (dissection or perforation)
- Distal thrombus embolization of pieces of the original thrombus "downstream" in the same vascular territory as the original thrombus (distal embolization)
- Blood vessel becomes acutely occluded (re-thrombosis/acute occlusion)
- Ischemia (reduced blood flow) in the brain
- Intra-cerebral hemorrhage (bleeding into the brain)
- False aneurysm formation

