- Neurological deficits, including a new stroke
- Death

Refer to the sample Instructions for Use (IFU) in **Appendix E** for table of previously observed rates of procedural risks.

Only trained and experienced physicians will use this device within the trial. The investigational device will be used as per the steps listed within the current Instructions for Use.

However, since the time window in which the device will be used within this study is expanded to between 6 - 24 hours after stroke symptom onset or time last seen well,

Document Number: CDM10000146

participation in the study adds a currently unknown level of risk to the subjects who are randomized to the Treatment arm. Some publications have reported increased rates of cerebral edema, intracranial hemorrhage, and mortality in patients treated with revascularization therapy beyond 6 hours. However other publications have not confirmed this finding, and the potential benefits of Trevo thrombectomy include revascularization, and revascularization has been shown to be correlated with improved clinical outcomes and reduced mortality, [17] therefore potential benefits outweigh the anticipated risks.

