5.3. Analysis of Primary Safety Endpoints

Both Arms:

Incidence of stroke-related mortality at 90 days will be presented by providing the count and percentage for each treatment arm. The difference in the percentage between two arms and the 95% CI for the difference will be calculated using the normal approximation to binomial. P-values will be calculated by the Chi-squared test or Fisher's exact test as appropriate. Relative Risk (RR) was provided as Trevo thrombectomy plus medical management / medical management.

ITT population will be used for the analysis of Primary Safety Outcome.

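### The definition behind the only primary safety outcome does not name death from the index procedure or device, so non-stroke procedural deaths leave the Trevo arm's count alone

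*Protocol*

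**What the plan says.** Protocol 4.3 lists one primary safety outcome for both arms: "Incidence of stroke-related mortality at 90 days". SAP 5.3 makes it a two-arm comparison in the ITT population. It asks for counts and percentages by arm, a risk difference with 95% CI, a chi-squared or Fisher p-value, and a relative risk.

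The meaning of stroke-related comes from Protocol Appendix B: "Death related to the index stroke; to systemic complications associated with the index stroke, or a new stroke". The SAP gives no definition of its own.

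Three other places bear on who can have a procedural death:

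- **Control treatment.** Appendix B says that "medical management as the label for the Control arm means no intra-arterial intervention with drugs or devices".
- **Crossover.** Protocol 5.3 says: "After randomization, no crossover is permitted".
- **Known risks.** Protocol 12.2 lists bleeding, infection and death for diagnostic angiography. For the retriever it lists access-site bleeding, access-site infection or sepsis, "Neurological deficits, including a new stroke", and death.

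**The concern.** A safety comparison between a procedure and no procedure should count the deaths that the procedure causes. Here the cause-specific definition has three routes in: the index stroke, its systemic complications, and a new stroke. A fatal complication at the arterial access site fits none of them.

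The index procedure is confined to one arm by design, so this gap can move the primary safety comparison in only one direction, towards the device. Non-stroke deaths unrelated to the procedure, such as an unrelated cardiac death, are also left out, but that can happen in either arm.

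At stake is the reading of the headline safety result. A relative risk near or below 1 for stroke-related death could sit beside a small excess of procedural deaths that the same table does not show.

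**Working it through.** The documents state no expected rate, margin or power for this outcome, so there is no planned figure to reproduce. The check is a comparison of texts followed by an illustration of size.

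**Step 1. Trace one death.** Take a Trevo subject who dies on day 10 of access-site sepsis.

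| Where it might count | Counted? | Source |
|---|---|---|
| Stroke-related death (primary safety, two-arm, ITT) | No | Appendix B; SAP 5.3 |
| Intra-procedural mortality (Trevo arm only) | No; limited to death during the procedure | Appendix B; SAP 3.1.4 |
| Procedure- and device-related SAEs (Trevo arm only) | No; window ends at 24 (-6/+24) hours | SAP 5.4 |
| All-cause mortality (secondary effectiveness, two-arm) | Yes, if the subject is in the enriched population | SAP 4.15.5 |
| 90-day mRS of 6 (primary efficacy) | Yes, under the same condition | SAP 4.14 |
| SAE summaries by arm and by relationship | Yes, as the event that led to death | SAP 5.2 |

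**Step 2. Intracranial procedural deaths.** Appendix B describes a stroke as lasting at least 24 hours, requires new symptoms for at least 24 hours for a hemorrhagic stroke, and requires a deficit still detectable at 24 hours for an ischemic one. A procedural hemorrhage or embolus that kills after that time can count as a new stroke. A perforation that kills within hours does not clearly qualify.

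**Step 3. Populations.** Primary safety uses ITT, which SAP 4.10 defines as all randomised subjects. SAP 6.3 uses all subjects as the denominator for safety events. Secondary effectiveness endpoints, including all-cause mortality, use the enriched population (SAP 4.15.5). Without enrichment the two sets coincide. With enrichment, no planned two-arm comparison of all-cause mortality covers everyone randomised.

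**Step 4. Size.** Inputs:

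- At most 250 subjects per arm (Protocol synopsis).
- Planning control proportion with mRS 6 of 0.19 (Protocol Table 6). This is all-cause death.
- Proportion x of Trevo subjects who die of a non-stroke procedural or device cause. The documents do not give x; I assume 0% to 2%.

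Deaths omitted = 250x. Suppose that all-cause mortality is truly equal at 19% and that every other death is stroke-related. The primary safety outcome would then show a relative risk of (0.19 - x)/0.19 where the all-cause value is 1.00.

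| x | Deaths omitted of 250 | Trevo vs control shown | Relative risk shown |
|---|---|---|---|
| 0% | 0 | 19.0% vs 19.0% | 1.00 |
| 0.5% | 1.25 | 18.5% vs 19.0% | 0.97 |
| 1% | 2.5 | 18.0% vs 19.0% | 0.95 |
| 2% | 5 | 17.0% vs 19.0% | 0.89 |

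Conversely, if stroke-related mortality were equal at 19% and x = 2%, the outcome would show 1.00 where counting the omitted deaths gives 0.21/0.19 = 1.11.

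**Step 5. Scale against sampling error.** For 19% vs 21% with 250 per arm, the standard error of the difference is sqrt(0.19 x 0.81/250 + 0.21 x 0.79/250) = 0.036. A shift of 2 percentage points is about 0.02/0.036 = 0.56 standard errors. A two-sided 5% test would detect it with power of about 8%, so a non-significant all-cause p-value would not rule out an excess of this size.

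**The case against.** The case on the other side is substantial.

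- **These deaths are already compared between arms.** All-cause mortality is a pre-specified secondary endpoint with the same set of statistics. The CEC adjudicates all deaths, the DMC reviews mortality in both arms, and the enrollment hold after five consecutive deaths ignores cause (Protocol 13.2). This stands. A reader might infer that procedural deaths disappear from the trial; the documents do not support that.
- **The omission is not total.** The definition says related to, not caused by, and includes a new stroke, so many fatal intracranial hemorrhages or emboli could qualify. This stands, subject to the 24-hour wording. A reader might infer that every procedure- or device-related death is excluded; that goes too far.
- **Not every procedural hazard belongs to one arm.** Protocol 12.2 says that "Renal toxicity and idiosyncratic responses to the injected contrast medium including anaphylactic reactions have also been reported". Controls may also receive contrast, since CTA is allowed at baseline and at 24 hours. This stands. The clear one-sided examples are access-site bleeding and access-site sepsis.
- **The population difference is conditional.** It arises only if the trial enriches. This stands.
- **Later procedural events are still reported.** SAEs are collected through the 90-day visit and summarised by relationship to device and procedure. This stands, though SAP 5.2 does not promise a table of fatal events by cause.
- **No decision rule uses the outcome.** It has no margin or threshold, and study success rests on the mRS (SAP 4.2). This stands and limits the consequence to interpretation.
- **The rate is assumed, and 250 is a maximum.** This stands. Protocol 12.2 calls the angiography risks other than hematoma relatively low, and the range must include zero.

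None of this places a non-stroke procedural death in the primary safety comparison, or supplies an all-cause comparison in all randomised subjects after enrichment.

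**Conclusion.** The concern holds in a limited form. As written, the primary safety comparison leaves out non-stroke deaths from the index procedure or device, which can arise only in the Trevo arm, and it is unclear on rapidly fatal intracranial procedural deaths. Any resulting error favours the device.

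Over an assumed 0% to 2%, the omission is 0 to 5 deaths among at most 250 Trevo subjects, or 0 to 2 percentage points. The relative-risk figures also assume 19% all-cause mortality and that all other deaths are stroke-related. How the CEC charter treats borderline deaths is not in these documents.

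A reader might infer that the efficacy conclusion or the stopping rules are compromised. They are not: every death in the analysed population scores mRS 6, with utility weight 0. The defect is in the definition and presentation of the headline safety result. It should be corrected because the correction is small and uses deaths that are already adjudicated.

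**What to change.** Two changes:

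1. In Protocol Appendix B, extend the definition of stroke-related death with the words *or to the study device or index procedure or their complications*. This also settles the rapidly fatal intracranial cases, which would then count whether or not they meet the 24-hour wording.
2. In SAP 5.3, report 90-day all-cause mortality by arm, with the same statistics, in all randomised subjects whether or not enrichment has occurred. Place it directly beside the primary safety row. It needs no judgement on cause, which is useful because the CEC may be unblinded (Protocol 13.2).

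The cost is a protocol amendment with IRB/EC approval (Protocol 14.4), possible re-review of some deaths already adjudicated, one more table row, and a Trevo-arm figure that may be slightly less favourable. No new data are needed, because all deaths already go to the CEC.
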